WP2: Survey of FTSUGs and national stakeholders via semi-structured telephone interviews – months 6-11; AJ lead with coapplicants DK, JM, MA, RAsx2

This work package will provide a better understanding of what FTSUGs do within their organisations, by undertaking semi-structured telephone interviews with FTSUGs operating in Acute Trusts and Mental Health Trusts in England (n= 100) and national stakeholders (n=10) in the FTSUG process, e.g. designers of the system, those regulating and monitoring it, and those able to discuss how it relates in design and implementation to other monitoring systems, which will address the following research aims and objectives:

Aim a) To map varying approaches to implementing and configuring FTSUG roles across NHS England.

Aim b) To generate evidence of the extent to which the FTSUG role has been 'normalized' in organisations.

Objective 1. IMPLEMENTATION & USE: Assess the scale and scope of the deployment and work of FTSUGs in NHS England.

Objective 2. IMPLEMENTATION & GOVERNANCE: Assess how the work of FTSUGs is organised and operationalised alongside other relevant local and national roles with responsibilities for managing concerns.

Objective 3. EFFECTIVENESS: Evaluate the comparative effectiveness of different types of FTSUG roles in supporting 'freedom to speak up'.

Following feedback on the outline proposal from the HS&DR panel, we have chosen to undertake WP2 and WP3 with Acute Trusts and Mental Health Trusts. As care delivery organisations, Acute Trusts and Mental Health Trusts face comparable contextual and clinical factors when implementing the FTSUG role. In addition, these Trusts are collectively the most widespread care delivery organisations in England and, since October 2016 at the latest, have at least one FTSUG in post. The FTSUG role is also currently operational in Clinical Commissioning Groups (CCGs), Ambulance Trusts, GP practices and community providers. However, FTSUG implementation is variable, very recent or absent in these organisations, where there are also obvious operational differences to Acute and Mental Health Trusts which would make meaningful comparisons of the FTSUG role difficult to achieve.

WP2 Data collection during months 6 to 9: 110 interviews over 4 months (100 interviews with FTSUGs and 10 interviews with stakeholders, such as regulators, monitors and policy makers).

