FTSUGs (n=100) will answer the same set of questions which will help better understand the variable characteristics of the FTSUG such as their age, gender, ethnicity, experience, nature of employment (full or part time, substantive or secondment post), skills and training (both the training received and training needs), as well as the work system within which the FTSUG is embedded. This mapping of characteristics and roles is an important task, given that analysis of data published by NHS Employers and the National Guardian (2017) shows large variation in implementation of FTSUG roles across England. For example, the number of FTSUGs present in Acute Hospital Trusts and Mental Health Trusts range from one to eight. Some FTSUGs were recruited into the role following interview, others were elected by colleagues or personally approached to undertake the role, but not interviewed. There is variation too in staff grades for FTSUGs, which range from Band 3 to 8a, with the majority at Band 7. The amount of protected time to undertake the FTSUG role also shows large variation, ranging from those having less than one day per week for the role (70%), two to three days per week (22%) and more than four days per week (8%), with 81% undertaking the role alongside management, clinical roles or Chaplaincy and voluntary roles. Information about the number, type and experiences of employees disclosing concerns and any contribution made to learning resulting from disclosure will also be collected.

The culture of speaking up within the organisation will be briefly discussed in the final phase of the interview. For example, we will ask FTSUGs about how they communicate their presence to staff and any local speak up initiatives they have implemented and how these have been enacted. Consideration will be given to any factors that have restricted or enabled the normalisation of the FTSUG role within their organisation and whether FTSUGs perceive their role and speaking up as normalised, or not. Unintended consequences, such as the FTSUG role duplicating or inadvertently overturning, for better or worse, existing effective local “speak up” practices within an organisation, will be discussed. We will also explore how concerns are responded to, addressing important concepts and issues identified in the literature, such as the Deaf Effect and Hearer Action/Courage. Candidate items for telephone interview guide (to be further informed by evidence synthesis and NPT) include:

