- **Respondent demographics:** Location and role within the organisation. Age, gender, ethnicity, years of service, previous posts, training/education.
- **Organisational descriptors:** Organisation size, type, structure and academic status.
- **Organisational structure, process and policy relating to speaking up:**
 - Organisational structures and processes in place for employees to speak up and for hearing and responding to employee concerns.
 - Divisional structures, units and roles assigned with responsibility for responding to concerns.
 - Overview of actions taken in response to concerns, timescale for response.
 - New structures/processes/policies created by FTSUG and resources available to the FTSUG.
- **Evaluation of the local response and commitment to/normalising the FTSUG role:**
 - Examples of barriers/enablers to operationalizing the role and effective response to concerns.
 - Numbers, types and severity of concerns raised since FTSUG post created.
 - Degree to which speaking up activities have led to sustained local positive action.
 - Comparison of intended to actual outcomes/changes resulting from implementation of the role
 - Self-evaluation of the organisational culture and response to implementation of the FTSUG role.

Relevant Key Findings (KFs – see box 1) from the NHS National Staff Survey 2017 will be analysed to further understand some of the institutional characteristics within which FTSUGs work. NHS Staff Survey data

collection occurs annually between September and October, at which time all the FTSUGs in the relevant Trusts will have been in post for at least 12 months. KFs will be published in March 2018, thus available for use in WP2 starting August 2018. Significant differences (as defined and reported within the survey) in KFs between 2015, 2016 and 2017 for each organisation will be collected and analysed.

Box 1: Examples of key finding (KF) from the NHS National Staff Survey

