KF 6 Percentage of staff reporting good communication between senior management and staff; **KF 28** Percentage of staff witnessing potentially harmful errors, near misses or incidents in last month; **KF 24** Percentage of staff reporting most recent experience of physical violence in last 12 months; **KF 27** Percentage of staff reporting most recent experience of harassment, bullying or abuse in last 12 months; **KF 29**. Percentage of staff reporting errors, near misses or incidents witnessed in the last month; **KF 30**. Fairness and effectiveness of procedures for reporting errors, near misses and incidents; **KF 31**.

Publicly available sections of Care Quality Commission (CQC) inspection reports from 2016 onwards will also be collected. For example, the 'responsive', 'safe' and 'effective' sections of the inspection reports will be collected and analysed for evidence of how institutions deal with employee concerns. Importantly, the information from the staff survey and CQC inspection reports will be used to describe the contexts within which FTSUGs operate, rather than drawing direct causal relationships between the staff survey, inspection reports and the extent to which FTSUGs and a speaking up culture have been normalised. However, the total dataset collected in WP2 will be combined to provide a rich and thick description of similarities and differences in FTSUG role implementation, alongside institutional level descriptors of culture, context and speaking up activities by employees, enabling preliminary conclusions to be reached about FTSUGs work and how, when and how often staff concerns are raised.

WP2 Sampling

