The telephone interviews will be audio-recorded for two reasons. Firstly, although answers to the structured questions will be noted as the interview progresses, having an audio-recording will be useful where there may be confusion or inaccuracy with answers. Secondly, audio-recording enables transcription of answers to the semi-structured, qualitative sections of the interview. Analysis of the structured questions will initially explore how answers are distributed. For example, descriptive statistics and bar charts will help visualise the 'shape' of the data by describing and summarising categorical variables such as gender and professional background of the FTSUGs. Additionally, continuous data will be explored using frequencies and histograms and described using means and standard deviations if normally distributed and medians and interquartile ranges if non-normally distributed. These steps will help identify interesting or anomalous features within the data and prove useful in then generating cross-tabulations and scattergrams of the relationships between these characteristics and other variables. Thematic analysis is a common technique used in the analysis of qualitative data generated via semi-structured interviews. Specifically, the analytic process will involve:

- (i) Data management, using a spreadsheet to preserve respondents with their quantitative and qualitative responses.
- (ii) In-depth familiarisation of the interview transcripts followed by thematic analysis, guided by NPT generative mechanisms (see table 1), to identify the range of respondents' views about the extent and their experiences of organisational commitment to the role and resources, barriers to and enablers of

- role normalisation.

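### WP2 collects concerns as a running total since each post began, so any comparison of how often concerns are raised would be confounded with Trust size and post age

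*Protocol*

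**What the plan says.** The relevant statements are all in the Protocol's WP2 part.

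- **Item.** Among the topics on local response to the role, the guide lists "Numbers, types and severity of concerns raised since FTSUG post created". The list is provisional: "Candidate items for telephone interview guide (to be further informed by evidence synthesis and NPT) include".
- **Use.** At the end of WP2 data collection the combined dataset is described as "enabling preliminary conclusions to be reached about FTSUGs work and how, when and how often staff concerns are raised".
- **Objective.** WP2 is assigned Objective 3: "Evaluate the comparative effectiveness of different types of FTSUG roles in supporting 'freedom to speak up".
- **Analysis.** WP2 Data analysis begins with descriptive summaries, said to be useful for "generating cross-tabulations and scattergrams of the relationships between these characteristics and other variables". No rate, denominator or adjustment is mentioned.
- **Size and post age.** The organisational descriptors include "Organisation size, type, structure and academic status". The date a post was created is not among the WP2 items. Time in post and staff numbers appear under WP3 Settings/context and sampling, as possible considerations when choosing sites.
- **Respondents.** Trusts have between one and eight FTSUGs, and WP2 Sampling expects mostly one respondent per Trust. The item does not say whether the count is the respondent's own or the whole Trust's.

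**The concern.** How often something happens is a rate: events divided by the people and time that could produce them. The item records only the numerator, and lets the time behind it differ from Trust to Trust. A Trust with more staff or an older post will report a larger total even if its staff raise concerns at exactly the same rate as elsewhere.

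This matters because size and post age may well go with the features of the role that WP2 wants to compare. WP2 Sampling, for instance, connects multiple FTSUGs in one organisation with multiple sites. If larger Trusts tend to have more FTSUGs, a plot of total concerns against number of FTSUGs would show a relationship even if the arrangement made no difference.

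The problem lies in data collection. Size is gathered, so a denominator could be built later. A cumulative total cannot be cut back afterwards to a common period, and if the post-creation date is not asked for, even an average rate over the life of the post is unavailable from the WP2 data.

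**Working it through.** The Protocol gives no rate or exposure figure to reproduce, so the check asks how far raw totals could differ between two Trusts with the same underlying rate.

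**Inputs from the Protocol**
- Latest date by which these Trusts had a first post: "since October 2016 at the latest, have at least one FTSUG in post". No earliest date is given.
- Interviews start in month 6: "thus available for use in WP2 starting August 2018". They run over months 6 to 9, that is August to November 2018.

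**Assumptions (not in the documents)**
- Earlier post dates of April 2016, October 2015 and January 2015, the last as an outer bound for a role arising from the 2015 review.
- Ratios of Trust size of 2, 4 and 8.

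**Formula.** Expected total = rate × staff × months of accrual. With equal rates, the ratio of totals = (staff ratio) × (months ratio).

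**Step 1: interview date alone.** A post dating from October 2016 has accrued 22 months by August 2018 and 25 by November 2018. Ratio 25/22 = 1.14. For older posts it is smaller, for example 37/34 = 1.09 for October 2015.

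**Step 2: add post age.** The comparator is an October 2016 post seen in August 2018 (22 months).

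| Post created | Months to Aug 2018 | Ratio to 22 | Months to Nov 2018 | Ratio to 22 |
|---|---|---|---|---|
| April 2016 | 28 | 1.27 | 31 | 1.41 |
| October 2015 | 34 | 1.55 | 37 | 1.68 |
| January 2015 | 43 | 1.95 | 46 | 2.09 |

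**Step 3: add size.** Multiply the widest-gap ratios by the assumed size ratio.

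| Size ratio | April 2016 (31/22) | January 2015 (46/22) |
|---|---|---|
| 2 | 2.8 | 4.2 |
| 4 | 5.6 | 8.4 |
| 8 | 11.3 | 16.7 |

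These compare extreme pairs, not typical Trusts.

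**Step 4: which source dominates.** Take log size as uniform over the assumed range, post age as uniform over up to 6, 12 or 21 extra months, and interview date as uniform over 3 months. The variance of log size is (ln r)²/12, which is 0.040 for r = 2 and 0.36 for r = 8. The variance of log exposure is 0.005 to 0.037 from post age and 0.0014 from interview date. As shares of the sum, size accounts for 51 to 98%, post age for 1 to 47% and interview date for 0.3 to 3%.

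**Step 5: with a common window and a denominator.** Counts over the same months per 1,000 staff give a ratio of 1.0 for equal underlying rates, whatever the size, post age or interview date. The last four complete calendar quarters before month 6 would be July 2017 to June 2018. That window opens nine months after October 2016, so every Trust that had its post by then is covered in full.

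**The case against.** The strongest reply is that nothing is settled yet. The item is a candidate, WP1c sets aside months 3 to 5 to develop and pilot the guide, and the WP2 conclusions are called preliminary and largely descriptive. Turning a count into a rate is a choice normally left to an analysis plan. The Protocol never says outright that concern counts will be tabulated against role characteristics: its named examples there are gender and professional background. The team also has staff numbers and time in post in view, since both are listed for WP3 site selection.

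Much of this stands and limits the point. It does not remove it. The item is not silent about the period; it names one, and the one it names is unequal across Trusts. An analysis plan cannot recover a window or a date that was not asked about. Calling a conclusion preliminary does not turn a running total into a frequency, and the assigned comparative objective makes a comparison of totals a natural next step.

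Some stronger readings are not supported:
- A reader might infer that totals would reflect size and post age instead of the FTSUG model. They would be confounded with the model; a real model effect could still be present in them.
- A reader might take concern counts to be the main quantitative measure in WP2, or a driver of WP3 site choice. The Protocol does not say the first, and counts are not among the site-selection factors it lists.
- A reader might treat an eight-fold distortion as established. It rests on assumed dates and sizes and on a pair of extremes.

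**Conclusion.** The point holds as a weakness in how the count is defined. Followed as written, the item gives totals that cannot by themselves answer how often concerns are raised, and any comparison of them across role types would be confounded with Trust size and post age.

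Only the interview-date component follows from the Protocol's own dates, and it is minor: at most about 14%, for the latest starters. Post age contributes a factor of about 1.4 to 2.1 at the widest interview gap if the earlier posts date from somewhere between April 2016 and January 2015. Size multiplies that by whatever the true ratio of Trust sizes is, taken here as 2 to 8. The calculation assumes equal, constant rates and dates exposure from each Trust's first post. If respondents report only their own concerns, and later posts exist alongside the first, the periods could differ further.

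The change is worth making before the guide is piloted. It does not call the WP2 design into question.

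**What to change.** Keep the since-creation total as a description of activity to date. Add four elements to the item:

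1. The number of concerns in one fixed window common to all Trusts, for example the last four complete quarters before month 6.
2. The date the post was created.
3. The staff headcount.
4. Whether the count is the respondent's own or covers the whole Trust.

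Wherever the frequency of concerns is reported or set against FTSUG characteristics, use concerns per 1,000 staff per quarter from the common window, not raw totals. A count regression with a log staff-time offset is optional; a simple rate is enough for a descriptive survey of 100 FTSUGs. The common window is also preferable to dividing the running total by months in post, because that assumes a constant rate while the Protocol's theoretical framework expects implementation to vary over time.

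The cost is a slightly longer interview item and one derived variable. Organisation size is already to be collected, but the post-creation date would be a new question in WP2.

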To confront this serious issue, the FTSU Review (Francis, 2015) sets out 20 Principles to guide the development of 'a consistent approach to raising concerns throughout the NHS whilst leaving scope for flexibility for organisations to adapt them to their own circumstances' (p.6). A single 'overarching Principle' states that every NHS organisation should 'foster a culture of safety and learning in which all staff feel safe to raise concerns' (p.6). Of specific relevance to this proposal is Principle 11 ('Support'), which outlines the introduction of a new role in all NHS organisations, called Freedom to Speak Up Guardians (FTSUGs), supported by a National Freedom to Speak Up Guardian (NG). The introduction of FTSUGs is founded on three interlinked objectives; to positively influence employees to speak up by creating an environment where

¹ The terms whistleblowing/whistleblower, raising concerns and speaking up are commonly and interchangeably used in literature, policy and the media. This proposal, in the main, refers to speaking up and raising concerns which are frequently used in the NHS and academic literature, and only uses the term whistleblowing and its derivatives where others have referred to this term.

speaking up is 'part of the normal routine business of any well led NHS organisation' (p.12); to promote culture change that reverses the woefully long record of NHS employees being professionally and personally victimised for raising concerns and to ensure NHS organisations, both individually and collectively, learn from employees who speak up.

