Telephone interview responses will mostly be obtained at the level of one FTSUG response per Acute Hospital Trust and Mental Health Trust. However, where multiple FTSUGs are in post in the same organisation we may interview additional FTSUGs within the organisation, for example those working at other sites. The NG's office has helpfully agreed to assist with our recruitment of 10 FTSUGs from the 10 regional networks (North East, East of England, South West, Yorks and Humber, East Midlands, London, North West, West Midlands, South East Coast and Thames Valley/Wessex), which are coordinated by 2 National Guardian Engagement Managers. The regional networks meet regularly as sources of support for FTSUGs, where "sharing and learning" best practice is encouraged and facilitated. Details of the study will be disseminated by researchers directly to FTSUGs via attendance at regional network meetings and via FTSUG dedicated email lists. In addition, 10 interviews will be undertaken with national stakeholders in the FTSUG process, e.g. designers of the system, those regulating and monitoring it, and those able to discuss how the implementation of FTSUG roles relates in design and implementation to other monitoring systems. The total sample size will therefore consist of 100 FTSUGs and 10 national stakeholders.

WP2 Data analysis – alongside data collection with months 10 and 11 exclusively for analysis

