- Organisational and logistical factors which may influence the implementation and normalisation of the FTSUG role: whether one or more FTSUG is in post; length of time FTSUG has been in post; whether the FTSUG is full-time or part-time and/or role is combined with another role (e.g. lead nurse or human resource manager); the numbers of staff employed; whether FTSUGs cover multiple sites.
- Data from the NHS staff survey will be reviewed e.g. key findings which demonstrate significantly worsening or improving indicators of staff speaking up. CQC inspection reports can similarly provide useful historical or contemporary insights into speaking up cultures within an organisation.

Purposive sampling will be used to identify key informants, documents and stakeholders who are involved in the oversight and delivery of the FTSUG role and any related speak up initiatives. Snowball sampling will be used to include a sample of those employees who have spoken up via the FTSUG. However, interviewing FTSUGs and those that have engaged with FTSUGs offers only a limited perspective about the FTSUG role, and the culture of speaking up. Therefore, we will also recruit, via snowball sampling, those who may have raised concerns through other channels (e.g. a Trade Union), but have not been in contact with the FTSUG, and/or those who may not have spoken up about concerns, thus providing a better understanding why some may not have yet engaged with the FTSUG role. The views of others involved in employee concerns will offer invaluable insights into coordination, cooperation and commitment to the FTSUG role, as well as other insights, such as whether the implementation of the FTSUG role has displaced, for better or worse, historically effective ways of informally or formally raising and responding to concerns.

WP3 Data collection:

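### WP2 plans to conclude how often staff concerns are raised, but its only count of concerns comes from Freedom to Speak Up Guardians and cannot show the level or direction of speaking up in a Trust

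*Protocol*

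**What the plan says.** All references are to the Protocol.

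- **Conclusion planned.** Under WP2 Data collection, after Box 1 and the description of the inspection reports, the text says that "the total dataset collected in WP2 will be combined", "enabling preliminary conclusions to be reached about FTSUGs work and how, when and how often staff concerns are raised".
- **Count collected.** The candidate items for the telephone interview guide include "Numbers, types and severity of concerns raised since FTSUG post created". The preceding description of the FTSUG interview lists "Information about the number, type and experiences of employees disclosing concerns". No other WP2 item counts concerns.
- **Who answers.** WP2 Sampling states: "The total sample size will therefore consist of 100 FTSUGs and 10 national stakeholders". FTSUG responses will "mostly be obtained at the level of one FTSUG response per Acute Hospital Trust and Mental Health Trust", with additional FTSUGs possibly interviewed where a Trust has several. The WP2 text puts the number of FTSUGs per Trust at one to eight.
- **Other WP2 data.** Staff survey key findings and inspection report sections are collected to describe context, and the text disclaims direct causal inference from them.
- **Other routes.** WP3 Settings/context and sampling says that FTSUGs and the people who engaged with them give only a limited perspective, and it recruits "those who may have raised concerns through other channels (e.g. a Trade Union), but have not been in contact with the FTSUG". The same section and the WP2 interview description raise, as a question, whether the role overturns or displaces existing routes, for better or worse.
- **Use.** WP2 lists Objective 3, the comparative effectiveness of different types of FTSUG role. WP2 Data analysis plans cross-tabulations and scattergrams of respondent characteristics against other variables.

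**The concern.** The planned conclusion is about concerns raised by staff. The measurement is of concerns that an FTSUG knows about. These differ by whatever goes to line managers, unions, human resources or nobody, and WP2 does not count that part. The caution about the FTSUG's limited view appears only in WP3, which is qualitative and covers six sites, so it cannot supply the missing frequencies.

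The count also has no natural direction. A high figure may mean that staff feel free to speak, or that ordinary routes have failed them. A low figure may mean silence. It may also mean that speaking up has become "part of the normal routine business of any well led NHS organisation" and rarely needs an FTSUG; this last reading is an inference, not something the Protocol states.

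At stake is the comparison of implementation models. If counts are set against FTSUG characteristics and read as amounts of speaking up, a model that diverts existing traffic to the FTSUG would look more productive than one under which local routes work well. Putting the count on a per-staff or per-year basis would not cure this, because the rate would still cover only what reaches the FTSUG.

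**Working it through.** **The plan's own figure.** Reading WP2 Sampling as 10 FTSUGs from each of 10 regional networks gives 10 × 10 = 100. Adding 10 national stakeholders gives 110 interviews, as stated. This total is not in dispute.

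**Does any WP2 source count concerns across routes?**

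| WP2 source | What it gives | All-route count? |
|---|---|---|
| FTSUG interview item | Number, type and severity since the post was created | No: answered by FTSUGs, scope and period not fixed |
| National stakeholder interviews | Design, regulation and monitoring of the system | No |
| Staff survey KF 29 | Percentage reporting errors, near misses or incidents | No: a percentage, incidents only |
| Staff survey KF 24, KF 27 | Percentages on violence, and on harassment, bullying or abuse | No: percentages, those topics only |
| Inspection report sections | Evidence of how institutions deal with concerns | No |

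The count starts when the post was created, so it has no earlier baseline that could reveal diversion, and its length varies with time in post.

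**What the count identifies.** Let T be all concerns raised in a Trust and s the share that reaches the FTSUG. Then

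FTSUG count = T × s.

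The Protocol gives neither T nor s. The values below are assumptions that show the range.

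| Case | T before → after | s before → after | FTSUG count | Change in count | Change in T |
|---|---|---|---|---|---|
| a | 200 → 200 | 10% → 30% | 20 → 60 | × 3 | none |
| b | 200 → 150 | 10% → 30% | 20 → 45 | × 2.25 | −25% |
| c | 200 → 300 | 30% → 10% | 60 → 30 | × 0.5 | +50% |

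In case a the count moves and the total does not. In cases b and c they move in opposite directions. The same arithmetic applies to two Trusts with different shares at one time.

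The level is equally open. A count of 100 implies T = 100 / s: 2000 at s = 5%, 1000 at 10%, 500 at 20%, and 200 at 50%.

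**Coverage within the FTSUG route.** The item does not say whether it means the respondent's own cases or those of all FTSUGs in the Trust. If a respondent reports only their own cases and k FTSUGs share the work equally (both assumptions), the answer covers 1/k of that route: 100% for k = 1, 50% for k = 2, 25% for k = 4, and 12.5% for k = 8.

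**The case against.** The strongest reply is that the conclusion rests on the whole WP2 dataset and not on the count alone. That dataset includes survey measures not tied to the FTSUG, inspection evidence, and interview items on all structures for speaking up. This is true as far as it goes. But the survey measures are percentages on particular topics, the text assigns them and the inspection reports to context, and nothing in the dataset counts concerns by route.

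It is also fair that the conclusions are called preliminary, that the interview items are candidates still to be piloted, and that WP3 seeks out people who used other channels, with five interviews per site for staff who had no contact with the FTSUG. The item is not expressly limited to the respondent's caseload, so single-route coverage is an inference from who answers. These points lower the stakes and make the change easy. They do not supply the missing measurement.

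Three stronger readings are tempting, and the document supports none of them:

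- A reader might infer that the plan expects the role to displace other routes. It asks whether this happens, in either direction.
- A reader might infer that the FTSUG count drives the choice of case sites. Sites come from the analysis of WP2 data in general, and the listed considerations are FTSUG numbers, time in post, working pattern, staff numbers, multiple sites, survey findings and inspection reports. The count is not among them.
- A reader might infer that WP2 ranks Trusts by count, or treats a higher count as success. No such analysis or reading is stated.

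**Conclusion.** The concern holds in a limited form. The planned conclusion about how often staff raise concerns is wider than the WP2 data can support. With an unknown FTSUG share, the count fixes neither the level of speaking up in a Trust nor the direction of a change or difference. Because WP2 is given the comparative-effectiveness objective and plans cross-tabulations, the limit needs to be written down before models are compared.

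The size of any distortion cannot be derived from the document. The threefold rise, the halving, the tenfold span of implied totals (200 to 2000) and the 12.5% coverage rest on assumed totals, shares and caseloads, and show only what is possible. The finding itself rests on two readings: that an FTSUG mainly reports what reached the FTSUG route, and that no WP2 source counts the rest. The point should be corrected, but it does not undermine the study, whose WP2 output is descriptive and preliminary.

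**What to change.** 1. In the WP2 Data collection paragraph on the combined dataset, limit the frequency conclusion to how often concerns are brought to FTSUGs.
2. In the interview guide, make the counting item ask for concerns brought to all FTSUGs in the Trust over a stated period, the same for every Trust. For that period, also ask for the number recorded through the Trust's other formal routes, where such a figure is held. Request both before the call.
3. State under WP2 Data analysis that a higher or lower FTSUG count alone is not read as better or worse when implementation models are compared.

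The cost is small: a few sentences, one extra interview item, and a narrower stated conclusion. The guide has yet to be finalised and piloted, so the item can be added there. The remedy is partial. Some Trusts will not hold the other-route figure, and where they do it will miss informal conversations with line managers. That is why the narrower wording is needed even if the extra figure is collected.
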